- 9. Grade 3 or higher recent (within the past 6 months) or ongoing bleeding events.

10. Symptomatic or uncontrolled cardiovascular disease, myocardial infarction or severe/unstable angina within the past 6 months, or New York Heart Association Class III or IV congestive heart failure

c. Donor eligibility

Eligible donors will include healthy sibling, relative or unrelated donors that are matched with the patient at HLA-A, B, C, and DRB1 by high resolution typing as defined by the Collaborative Trials Network²⁹.

V. Study Design

1. Sample size

a. A total of up to 12-18 evaluable patients will be enrolled in phase I. The 6 patients treated at the MTD (or lowest biologically active dose) in phase I will be analyzed among those treated in phase II. In phase II, 24 evaluable patients will be enrolled to study CD4+ T-cell STAT3 phosphorylation at the MTD. Additional 14 evaluable patients will be accrued to expansion stage if 9 or less of the initial patients treated at the MTD develop grade II-IV acute GVHD. Thus, a total of up to 50 evaluable patients could be enrolled to the combined phase I and II components of the trial. We anticipate up to 63 total could be enrolled and treated with PAC/SIR/TAC (which would account for a 10% replacement for non-evaluable subjects in phase II, and possible 10 subjects non-evaluable in the phase I component of the trial).

Withdrawal

- a. Subject withdrawal from the study will take place under the following circumstances:
 - i. those patients who sign consent for the study, but fail to initiate treatment on account of:
 - 1. denial of coverage from insurance provider
 - 2. death prior to initiation of treatment
 - 3. withdrawal of patient consent at any time after therapy

Subjects who withdraw consent for pacritinib therapy after day +21 but before day +100 will be asked to continue on study for follow-up of their condition and allow collection of research blood samples. These patients will be considered "off-therapy, on-study" reflecting **partial** withdrawal of consent. These patients will inform the secondary endpoint of GVHD prevention, and only be excluded from the analysis if they are off pacritinib for more than 4 weeks and do not resume the drug thereafter for causes other than acute GVHD (treatment failure). Subjects who withdraw consent for pacritinib therapy before day +21 will be excluded from any study analysis reflecting **full** withdrawal of consent.

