An evaluable patient for the phase I portion of the trial must have either met one of the defined clinical events in the DLT definition, or if not, must have been receiving pacritinib within 72 hours of the planned day +21 blood sample for determination of pSTAT3 level. Those patients that have not had a clinical DLT event and are not actively taking pacritinib for any reason within 72 hours of day +21 will be considered not evaluable, and will be replaced.

The phase II component of this trial is designed to detect a significant change in the biologic endpoint of STAT3 activity at day +21. The preliminary data revealed that the

mean and standard deviation (SD) of CD4+ T-cell pSTAT3 activity among 18 HCT recipients at day +21 were ~50% and ~25%, respectively, regardless of acute GVHD severity. We conservatively anticipate that mean of pSTAT3 level at day +21 will decrease to 35% or less by combining PAC to SIR/TAC. With a two-sided significance level of 0.05, a total sample size of 24 will achieve 80% power to detect a decrease of 15% when the anticipated SD is 25%, which is equivalent to an effect size of 0.6. We anticipate that the actual SD will be lower than 25%. If the actual SD is 20%, the study will have 94% power to detect a difference of 15% (an effect size of 0.75).

We also aim to understand whether the observed incidence of grade II-IV acute GVHD is sufficiently promising to warrant further study in a trial adequately powered to address this clinical endpoint. Based on published and unpublished experience of over 300 treated-patients, the incidence of GVHD with SIR/TAC is 43%. We hypothesize that the cumulative incidence rate of GVHD with PAC/SIR/TAC by day +100 will reduce to 23% (a decrease of 20%) by day +100. The study expansion will be considered if 9 or less of 24 patients (37.5%) initially treated with PAC/SIR/TAC develop grade II-IV acute GVHD by day +100. The expansion will permit an additional 14 patients will be accrued.

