The expanded phase II trial (second stage of phase II) will be considered favorable if 12 or less of the total 38 (31.6%) patients develop acute GVHD by day +100. This sample size was computed using Simon's two-stage design with 10% one-sided significance level and 90% power. If this regimen is actually not effective, there is 9.8% probability of concluding that it is. If the regimen is actually effective, there is 8.6% probability of concluding that it is not. If the second stage is open (n=38), the study will achieve 95% power to detect a decrease of 15% when the SD is 25%. The Blood and Marrow Transplant Program at MCC performs approximately 190 allogeneic procedures annually. A conservative estimated accrual rate of 20% would provide at least 38 patients each year allowing for full accrual by 24 months.

An evaluable patient for primary endpoint is defined as patients who received PAC/SIR/TAC until at least day +21 of their alloHCT and who has neither relapsed nor died of any reasons without experiencing grade II-IV aGVHD until day +100. A non-evaluable PAC/SIR/TAC patient will be replaced and we anticipate 41 patients will be accrued to the interventional study in order to account for 10% of competing risks (relapse or death without GVHD) at day +100.

Additional 15 patients who receive the standard GVHD prevention regimen of SIR/TAC, will be enrolled for blood sample collection only (8 green top tubes of blood) on days +21 and +100 of the alloHCT. The amount of circulating Treg, Th1, and Th17 cells will be analyzed. The exact same eligibility criteria will apply for these subjects.

A total of up to 68 (up to 18 patients in phase I [with the 6 treated at MTD included among those analyzed in phase II] + 32 [PAC/SIR/TAC] + 3 [non-evaluable replacement] +15 [blood sample collection only]) patients will be enrolled.

Statistical analysis methods

Patient baseline characteristics will be summarized using descriptive statistics including mean, median, standard deviation and range for continuous measures and proportions and frequencies for categorical measures. As the primary endpoint of the study, one sample t-test will be employed to examine if pSTAT3 at day +21 is decreased by 15% from historic mean of 50%. A two-sided p-value of <0.05 is considered statistically

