^{*}The CTCAE v4 term 'left ventricular systolic dysfunction' and its grading are based on the degree of clinical manifestations and therapy needed to control this issue. In contrast, specific cut-off values for abnormal ejection fraction are not provided, and grades 1 and 2 AE have no other descriptors. Detail is only provided for grade 3 ("symptomatic due to drop in ejection fraction responsive to intervention"). To be included on this trial, patients must have at least an ejection fraction of 45%. Adhering to accepted definitions of LV systolic dysfunction, we will consider a decline in LV ejection fraction to less than 40% as an event worthy of holding pacritinib therapy (and treat this as the equivalent of grade 2 per above). To resume therapy, a repeat echocardiogram within 14 days of stopping pacritinib must show return to > 45% ejection fraction.

After dose reduction, no dose re-escalation is allowed.

Management of Gastrointestinal Toxicity

The need for managing GI effects of pacritinib, particularly diarrhea, should be anticipated. A careful baseline evaluation of bowel habits (frequency and consistency of bowel movements) should be obtained at baseline for all patients.

Dose reduction rules for pacritinib (combined with SIR/TAC)		
Diarrhea	Current Dose (pacritinib)	Dose Reduction (pacritinib)
None / responds to antimotility agents	200mg twice a day	N/A
≥1500ml/day x3 days*	200mg twice a day	200mg qAM and 100mg qPM
	200mg qAM and 100mg qPM	200mg daily
	100mg twice a day	Hold pacritinib until stools are formed or volume is <500ml/day, then resume at 100mg twice a day and continue until day +70 taper. If diarrhea (≥1500ml/day x3 days) returns after holding pacritinib and does not respond to antimotility agents, patient comes "off-drug" but remains "on-study" for data collection and research labs.
	100mg daily	Hold pacritinib until stools are formed or volume is <500ml/day for at least 5 days, then resume at

^{**}As per above, symptomatic heart failure (grades 3 and 4 per CTCAE ver4) require complete discontinuation of pacritinib.

	100mg a day and continue until day +70 taper. If diarrhea (≥1500ml/day x3 days) returns after holding pacritinib and does not respond to antimotility agents, patient comes "off-drug" but remains "on-study" for data collection and research labs.
mote diarriea must be non-ini	ectious and unresponsive to anti-motility agents

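### Two conflicting rules on stopping pacritinib decide who counts toward the ≤9/24 and ≤12/38 GVHD rules, and neither protects GVHD that leads to stopping before day +21

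*Combined protocol and SAP*

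**What the plan says.** **Section V, Withdrawal.** Patients who withdraw consent for pacritinib after day +21 and before day +100 are asked to stay in follow-up and contribute to the GVHD endpoint. They will "only be excluded from the analysis if they are off pacritinib for more than 4 weeks and do not resume the drug thereafter". The sentence then limits this to causes other than acute GVHD; a stop because of GVHD is treatment failure. Withdrawal of consent for the drug before day +21 is full withdrawal, with exclusion from every analysis and no GVHD exception.

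**Section V.7, Statistical considerations.** "An evaluable patient for primary endpoint is defined as patients who received PAC/SIR/TAC until at least day +21 of their alloHCT", provided also that they did not relapse or die without grade II-IV GVHD by day +100. "A non-evaluable PAC/SIR/TAC patient will be replaced", and 41 patients are planned to obtain 38. There is no 4-week rule and no exception for GVHD that ends treatment before day +21.

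**Decision rules, Section V.7.** The null rate is 43% and the hypothesized rate 23%. "The study expansion will be considered if 9 or less of 24 patients (37.5%) initially treated with PAC/SIR/TAC" develop grade II-IV GVHD. The expanded trial "will be considered favorable if 12 or less of the total 38 (31.6%) patients develop acute GVHD by day +100". Trial Design adds that the primary endpoint must also be met.

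**Section VI.3, gastrointestinal toxicity.** At the two lowest doses in the table, a patient whose diarrhea recurs after a hold and does not respond to antimotility agents comes off drug but "remains 'on-study' for data collection and research labs".

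**The concern.** The clinical question is whether giving PAC/SIR/TAC lowers grade II-IV GVHD by day +100 below 43%. A count filtered on staying on drug answers a different question, and here the filter itself is not fixed.

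Take two patients who stop pacritinib at day +35 and develop grade II-IV GVHD at day +80. If one withdrew consent for the drug, Section V, Withdrawal, removes that patient while Section V.7 keeps the patient as evaluable. If the other stopped under the diarrhea rule, that patient stays on study and, under Section V.7, counts as a failure. Next take a patient with grade II-IV GVHD at day +15 who then comes off drug. Read literally, Section V.7 makes this patient non-evaluable and replaceable, although the Withdrawal text treats stopping for GVHD after day +21 as failure.

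GVHD is labelled secondary, but it gates the expansion and is half of the definition of a favorable result. One case can decide it: 13/38 becomes 12/38 if a patient with GVHD is replaced by one without.

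**Working it through.** **1. Who counts, by time and reason of stopping**

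| Situation | Section V, Withdrawal | Section V.7 |
|---|---|---|
| Consent for drug withdrawn after day +21, off more than 4 weeks, cause other than GVHD | Excluded | Evaluable, not replaced |
| Stop after day +21 because of GVHD | Kept, as failure | Kept |
| Consent for drug withdrawn before day +21 | Excluded from every analysis | Non-evaluable, replaced |
| Off drug before day +21 for another reason, including GVHD | Not addressed | Non-evaluable, replaced |

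Row 1 is a contradiction. Rows 3 and 4 can remove a GVHD event.

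**2. Does the Section V.7 definition govern the GVHD count?** It is labelled as being for the primary endpoint, which is pSTAT3. However, it uses the day +100 GVHD outcome and drives the accrual of 41 for 38. Section V.1 describes the 24 and the additional 14 as evaluable patients. No other GVHD set is defined.

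**3. Reproducing the plan's error rates.** Inputs from Section V.7: p0 = 0.43, p1 = 0.23, ≤9 of 24, then ≤12 of 38.

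P(favorable | p) = Σ over x ≤ 9 of Bin(x; 24, p) × P(Bin(14, p) ≤ 12 − x)

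- p = 0.43: 0.0984 (stated 9.8%).
- p = 0.23: 0.9139, so type II error 0.0861 (stated 8.6%).

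The design arithmetic is correct.

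**4. Removal with replacement.** Let s be the share of treated patients removed and g the GVHD rate among them. Both are assumptions; the documents give neither. At a true rate of 43% among all treated, the evaluable rate is

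p_e = (0.43 − s·g)/(1 − s).

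| s | g | p_e | P(favorable) |
|---|---|---|---|
| 10% | 23% | 0.407/0.90 = 45.2% | 5.9% |
| 10% | 43% | 0.387/0.90 = 43.0% | 9.8% |
| 10% | 60% | 0.370/0.90 = 41.1% | 14.5% |
| 10% | 100% | 0.330/0.90 = 36.7% | 30.8% |
| 5% | 100% | 0.380/0.95 = 40.0% | 17.9% |

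**5. Removal without replacement.** A row 1 patient is evaluable under Section V.7 and so would not be replaced. If such patients are then dropped and ≤12 is applied to 36 or 34 in total (first stage still 24), P(favorable | 0.43) is 14.7% or 20.8%, even if removal is unrelated to GVHD.

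**6. The opposing filter.** Section V.7 also removes relapse or death without GVHD, and allows 10% for it. These are non-events.

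- Alone: p_e = 0.43/0.90 = 47.8%, P(favorable) = 3.0%.
- With a further 5% removed, all with GVHD: 0.38/0.85 = 44.7%, 6.7%.
- With a further 10% removed, all with GVHD: 0.33/0.80 = 41.3%, 14.1%.

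**The case against.** A reader might infer from the 4-week sentence that any GVHD which causes a patient to stop can be deleted. The documents do not support that. After day +21, the Withdrawal text keeps such patients as failures and Section V.7 keeps them as evaluable. The gap exists only before day +21.

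Nor does the 4-week sentence plainly reach toxicity stops. Read literally, it covers withdrawal of consent for the drug. A model that removes every patient who stops would overstate it.

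The diarrhea rule might suggest that gut GVHD routinely leads to exclusion, because its threshold of ≥1500 ml/day is close to the >1500 ml/day of stage 3 gut GVHD in Appendix A. But the rule requires three days of non-infectious diarrhea unresponsive to antimotility agents. Its actions are dose reductions or temporary holds, and permanent discontinuation follows only on recurrence. Nothing requires pacritinib to stop at GVHD. What remains is a risk that the reason for stopping is misattributed.

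The Section V.7 definition is labelled for the primary endpoint, so applying it to GVHD is an inference. The inference stands because replacement and accrual depend on the definition and there is no alternative.

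The largest figures assume that every removed patient had GVHD. Removing 5% or 10% of treated patients in this way means 12% (5/43) or 23% (10/43) of all GVHD cases. Removal can also be neutral or conservative, and the relapse/death filter raises the observed rate. Finally, these figures concern the GVHD rule alone; a favorable result also needs the pSTAT3 endpoint, and Section V.7 seeks only a signal for a later powered trial.

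**Conclusion.** The concern holds in a limited form. The two sections contradict each other on patients who withdraw consent for pacritinib after day +21 and stay off it more than 4 weeks for a cause other than GVHD. Neither protects GVHD that leads to stopping before day +21. The same data can therefore give two different counts against ≤9/24 and ≤12/38.

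The stated 9.8% is correct for the design as drawn. It carries over to the filtered count only if removal is unrelated to GVHD and removed patients are replaced. With 10% removed and replaced, the assumed scenarios span 5.9% to 30.8%. It would be tempting to conclude that the false-positive rate is inflated; the documents do not establish this, because they give no stopping rates and the relapse/death filter works in the opposite direction. The established defect is an undefined analysis set, with an error rate that cannot be stated until it is defined.

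**What to change.** - Reconcile Section V, Withdrawal, with Section V.7 through one set for the GVHD endpoint and both decision rules: all patients who received pacritinib at the phase II dose, including the phase I patients carried forward. Count grade II-IV GVHD from day 0 to day +100 whether or not pacritinib was stopped, and whatever the reason.
- Delete the 4-week exclusion for this endpoint, and limit the day +21 treatment condition to pSTAT3.
- Censor patients who refuse further follow-up in the cumulative incidence estimate, and report their number. Follow-up after stopping is requested only of those who withdraw after day +21, so earlier withdrawals may lack data.
- Apply the cut-offs to the first 24 and first 38 treated patients in order of enrolment, or restate the exact error and power for the number treated. For example, keeping ≤9 of 24 and then ≤12 of 41 gives 5.0% error and 86.6% power.
- Report the on-drug subset as a sensitivity analysis.

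Section V.6 says that accrual is complete, so the expansion decision and past replacements cannot be undone. The change applies to the final count and report. The cost is wording, and possibly a less favorable observed rate.

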(Dose level 1) PAC 100mg po daily, (Dose level 2) PAC 100mg po twice daily, and (Dose level 3) PAC 200mg po twice daily. Dose cohort 1 (PAC 100mg daily) represents the lowest dose level that would potentially inhibit CD4+ T-cell pSTAT3. This is based on PK/PD data from the completed phase I trial of pacritinib in lymphoma⁷. For all patients enrolled in the phase I portion of this study, pharmacokinetic sampling of plasma pacritinib levels will be drawn on days 0 and +21 at the following time points: predose. +4 hours. +12 hours. and +24 hours (window of +/- 1 hour on each timed PK sample). Pharmacodynamic, CD4+ T-cell pSTAT3 values will be assessed at baseline and day +21 as well. EKGs (on days 0 and +21) will be performed pre-dose and at 4 hours (pacritinib Tmax)⁷ – with +/- 1 hour window on the 4-hour post-dose EKG. The initial group of 3 patients will be enrolled in cohort 1. Dose escalation of pacritinib will proceed according to the following: If no DLT is observed among 3 patients in a cohort AND the average %pSTAT3+ CD4+ T-cells are >35% at day +21, the next group of 3 will be treated at the next highest dose level. If the current level (i.e., the level at which no DLTs are observed) is the highest dose level, three additional patients will be enrolled (total of six). If one DLT is observed among 3 patients in a cohort, the next group of 3 will be treated at this same dose level. If no more DLT is observed among the 3 additional patients (i.e. one DLT in total is observed among the 6 patients) AND the average %pSTAT3+ CD4+ T-cells are >35% at day +21, then the next 3 patients will be treatment at the next highest dose level. If at least 1 more DLT is observed among the 3 additional patients, then the MTD is exceeded. If 6 patients have been treated at the next lower dose level, it will be considered as the MTD. If not, three additional patients will be enrolled. This escalation approach will then be continued until MTD or a tolerated dose (≤1/6 DLT) is identified at which <35% of the CD4+ T-cells are pSTAT3+.on day +21 (see Table 1). That dose will be considered to be the recommended phase II dose. The total number treated on the phase I component will depend on the occurrence of dose limiting toxicity (DLT) or the average frequency of pSTAT3+ CD4+ T-cells at day +21 in a cohort, however the maximal number accrued on the phase I study would approximate 12 to 18 total evaluable subjects. Patients in the phase I component of the trial will be monitored throughout their 100 days of pacritinib therapy for DLT events, however the minimum DLT observation period required prior to escalation to higher dose levels in the phase I component is 30 days from the last patient's (within dose level) initiation of pacritinib therapy. In addition to informing the recommended phase II dose, the PK/PD data from days 0 and +21 will be used to identify any dose-dependent patterns among serum pacritinib concentrations and 1) CD4+ T-cell STAT3 phosphorylation, 2) Treg reconstitution, 3) QTcF prolongation, or 4) changes in plasma tacrolimus and sirolimus levels.

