Subjects who do not wish to permit follow-up of their condition and continued collection of their peripheral blood for research studies will also be called **full** withdrawal of consent.

Withdrawal of consent (partial or full) will be documented in OnCore and within the patient's medical record.

3. Intervention: Pacritinib

a. Dose and Schedule: Up to 200mg BID orally (or MTD) from day 0 until day +100. PAC will be tapered to 50% of the total dose at day +70, then 25% of total dose at day +84, then stop at day +100 (+/- 7 day window is provided around timing of tapering events at day +70 and day +84, as well as last dose stop date around day +100).

4. Standard transplant care and practice

a. Donor selection

Donor must be a sibling, relative, or unrelated donor identical for HLA-A, -B, -C, and HLA-DRB1 by high resolution typing methods.

- b. Stem cell mobilization and collection
- 1. Peripheral blood stem cell mobilization: Donors will be mobilized and collected per institutional or National Marrow Donor Program (NMDP) standard operating protocol. The desired target CD34+ cell dose is $5-10 \times 10^6$ cells/kg. Collection of $<5 \times 10^6$ CD34/kg is not a deviation.
- 2. Umbilical cord blood, HLA haploidentical, and bone marrow stem cells grafts are not included in this protocol.

c. Conditioning regimen

The conditioning regimen is per physician discretion but restricted to busulfan and fludarabine or melphalan and fludarabine. The specific details of these two regimens will adhere to BMT Program standards.

Version 8.0 14

d. GVHD prophylaxis

In addition to the study drug, pacritinib, SIR/TAC will be administered and dosed according to Moffitt Cancer Center, Department of Blood and Marrow Transplantation standard practice. Attending physician discretion is permitted with regard to timing, rapidity, and completion of SIR/TAC taper. SIR/TAC levels will be monitored according to program standards. The therapeutic target for SIR is 5-14 ng/ml. The therapeutic target for tacrolimus is 3-7 ng/ml. It is expected that pharmacologic fluctuations of SIR and TAC levels may occur during this treatment, and such fluctuations in dose levels outside the target ranges will not be considered a deviation. Dose modifications of SIR/TAC for concurrent use of CYP3A4 inhibitors or inducers will be based on program standards.

Note: Pacritinib is neither an inhibitor nor an inducer of cytochrome P450 (CTI BioPharma Investigator Brochure).

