- 4. Pharmacokinetic (PK) parameters: For all patients enrolled in the phase I portion of this study, pharmacokinetic sampling of plasma pacritinib levels will be drawn on days 0 and +21 at the following time points: pre-dose, +4 hours, +12 hours, and +24 hours.
- Analysis of tissue-infiltrating immune cell subsets: We will obtain available GVHD target organ (e.g. skin, liver, GI) biopsy samples to study tissue-infiltrating CD4 T cell subsets (Th1, Th2, Th17, Treq) through tissue IHC (immunohistochemistry). These biopsies were obtained as part of routine clinical practice for GVHD diagnosis, and these available resources only will be used for this purpose (i.e. no clinical trial-specific biopsies will be obtained). At time of this protocol amendment when trial accrual is now complete, we expect approximately 25 total representative samples (respecting biopsy samples from skin, and GI sites including gastric, duodenal, and rectum) available to be included in this analysis. We will also enlist 25 representative historical control subject GVHD biopsy samples for comparison, arising from patients previously treated with standard of care sirolimus/tacrolimus GVHD prevention off-protocol. These will also be obtained from existing historical biopsy samples (no new biopsies to be performed). From these available biopsy samples, slides will be prepared, tissue stained for Thsubset markers (CD4/Tbet, CD4/GATA3, CD4/RORy, and CD4/FoxP3), and data acquired in collaboration with the Moffitt Pathology department, Tissue/Histology Core, and Image Analysis Core. Statistical comparisons will be made across pacritinib trialtreated subjects vs. standard of care off-protocol subjects to discern any differences. Other variables considered in this analysis will include clinical GVHD stage, time from transplant, and pathologic GVHD grade.

7. Statistical considerations

Clinical trial design, power calculations, and analysis

Phase I consists of a standard 3+3 design with three PAC dose cohorts. The DLT definitions are described on page 9 of this protocol. The MTD is defined as the highest dose level at which one or none of 6 subjects develop a DLT, and the combination of safety and biologic activity of pacritinib will dictate selection of recommended phase II dose. A total of 12-18 patients will be enrolled to determine the PAC MTD. Patients treated at the MTD (or lowest biologically active dose) in phase I will be analyzed among those treated in phase II.

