^{*}This total measured stool volume of > 1500mL/day has been approximated to > 7 episodes of diarrhea per day (*Harris, et al. BBMT, 2016*) based on review of diarrhea volume and stool frequency of over 300 patients in this analysis. Thus, we will treat either this measured volume, or > 7 episodes of diarrhea per day (when volume is not measured) as the threshold requiring dose modification. This rule also harmonizes with CTCAE ver4, as this same frequency of stools constitutes grade 3 diarrhea.

General Administration Guidelines

Missed or Vomited Doses

Missed doses will not be replaced. All missed doses should be documented in the patient diary. If a dose is vomited within one hour of ingestion, it will be considered a missed dose and recorded as such on the patient diary. The dose will not be repeated that same day but the patient will follow regular schedule starting the next study dosing day. If vomiting occurs more than 1 hour after dosing, it will still be considered a complete dose.

SAFETY AND REPORTING REQUIREMENTS

ASSESSMENT OF SAFETY

Safety assessments will consist of monitoring and recording adverse events and serious adverse events and other protocol-specified tests that are deemed critical to the safety evaluation of the study drug(s) and should be consistent with institutional standards and Good Clinical Practice.

DEFINITIONS

Unanticipated Problems (UP)

A UP includes any incident, experience, or outcome that involves risks to patients that are 1) unexpected with relation to the planned study or intervention, 2) related or possibly related to the research study or intervention, and 3) places patients at more risk than anticipated. For the purposes of this clinical study, UPs include only treatment-emergent problems which are either new or represent detectable exacerbations of pre-existing conditions.

Adverse Events (AE)

An AE is any unfavorable and unintended sign, symptom, or disease temporally associated with the use of an investigational (medicinal) product or other protocol-imposed intervention, regardless of attribution. For the purposes of this clinical study, adverse events include only treatment-emergent events which are either new or represent detectable exacerbations of pre-existing conditions.

This includes the following:

Version 8.0 27

- Subjective or objective symptoms spontaneously offered by the subject and/or observed by the investigator or study staff including laboratory abnormalities of clinical significance.

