- "Reasonable Possibility", for the purposes of safety reporting, means there is evidence to suggest a causal relationship between the drug and the adverse event. Examples of evidence that would suggest a causal relationship between the drug and the adverse event are:
- A single occurrence of an event that is uncommon and known to be strongly associated with drug exposure.
- One or more occurrences of an event that is not commonly associated with drug exposure, but is otherwise uncommon in the population exposed to the drug. If the event occurs in association with other factors strongly suggesting causation (eg, strong temporal association, event recurs on rechallenge), a single case may be sufficiently persuasive; but often, more than one occurrence would be needed before the sponsor could make a determination of whether the drug caused the event.

Unexpected

An "unexpected" AE is an AE that is not listed in the Investigator Brochure or is not listed at the specificity or severity that has been observed. "Unexpected" also refers to AEs that are mentioned in the Investigator Brochure as occurring with a class of drugs or as anticipated from the pharmacological properties of the drug, but are not specifically mentioned as occurring with the study drug under investigation.

DOCUMENTING AND REPORTING OF ADVERSE OR SERIOUS ADVERSE EVENTS AND UNANTICIPATED PROBLEMS

The Sponsor-investigator is responsible for ensuring that AEs, SAEs, and UPs that are observed or reported during the study, as outlined in the prior sections, are recorded on the study adverse event log

Version 8.0 29

with AE collection timelines adhering to the standards of the Institution. All SAEs also must be reported according to the local IRB guidelines as well as to the CTI PVG

Adverse Event and Unanticipated Problem Reporting Period

The AE and UP reporting period for this study begins after first dose of study drug administration until 30 days after discontinuation of the study drug. Grade 3 or greater AEs, SAEs, or UPs that are encountered during the protocol specified AE reporting period should be collected, and followed to resolution or until the patient is lost to follow up or withdrawals consent. Resolution/stable means the subject has returned to baseline state of health or the Investigator does not expect any further improvement or worsening of the event.

Assessment of Adverse Events and Unanticipated Problems

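### Patients who withdraw consent for pacritinib before day +21 are dropped from every analysis, safety included, and no planned all-treated AE/DLT summary brings them back

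*Combined protocol and SAP*

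**What the plan says.** **Section V, Withdrawal.** "Subjects who withdraw consent for pacritinib therapy before day +21 will be excluded from any study analysis"; this is classed as full withdrawal. A patient who gives up the drug between day +21 and day +100 is a partial withdrawal and stays in follow-up. Refusing follow-up is listed as a further route to full withdrawal: it covers "Subjects who do not wish to permit follow-up of their condition and continued collection of their peripheral blood for research studies".

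**Section V.7, phase I.** An evaluable patient "must have either met one of the defined clinical events in the DLT definition" or, failing that, must have been on pacritinib within 72 hours of the day +21 sample. Only patients without a DLT who are off the drug at that point, whatever the reason, are non-evaluable and replaced. On the dose, "The MTD is defined as the highest dose level at which one or none of 6 subjects develop a DLT". The Protocol design section adds: "If at least 1 more DLT is observed among the 3 additional patients, then the MTD is exceeded".

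**Section V.7, phase II.** "An evaluable patient for primary endpoint is defined as patients who received PAC/SIR/TAC until at least day +21 of their alloHCT", with a further condition on relapse and death without GVHD up to day +100.

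**Section VI, safety.** "Safety assessments will consist of monitoring and recording adverse events and serious adverse events" and other protocol-specified tests. The AE reporting period "begins after first dose of study drug administration until 30 days after discontinuation of the study drug".

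**The concern.** A rule that removes patients for stopping early is tolerable for a day +21 biomarker, which cannot be measured on drug in someone who has left it. It is not tolerable for safety, because the reason for leaving may be the event being counted.

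The protocol makes this plausible. It says pacritinib diarrhea usually starts within 7 days. It treats more than 7 episodes a day as grade 3. It counts any grade 3 or higher event at least possibly related to pacritinib as a DLT. A patient could reach that point well before day +21 and then decline the drug.

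At stake is whether the reported toxicity of pacritinib with sirolimus and tacrolimus covers everyone exposed. The literal wording also sits badly beside the phase I evaluability rule: a patient with a DLT on day +10 who then refuses the drug is evaluable under V.7 and excluded under Withdrawal.

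**Working it through.** The plan states no figure on this point, so the check is mainly a comparison of texts.

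**1. Does consent require the exclusion?** No. Refusing only the drug is partial withdrawal after day +21 and full withdrawal before it. Refusing follow-up is listed separately. A patient who declines only pacritinib on day +10 has not refused follow-up, yet gets the full-withdrawal label.

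**2. Do the safety data exist?** Yes, at least in part. Grade 3 or higher AEs and all serious AEs are logged from first dose to 30 days after the drug stops. Follow-up of an event may end if consent is withdrawn, but what was recorded before that date remains.

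**3. Does V.7 bring these patients back?**
- Its analysis methods cover baseline characteristics, pSTAT3, acute GVHD, overall and relapse-free survival, and T-cell subsets.
- It defines no safety population and lists no AE table.
- Its phase II evaluable population requires treatment to day +21, so early withdrawers fall outside that too.
- It uses DLTs in one place, the MTD definition.

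**4. Does the exclusion reach the phase I DLT count?** Probably not. The V.7 rule is specific to phase I, makes a DLT sufficient for evaluability, and replaces only DLT-free patients. Phase II has no corresponding rule.

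**5. How the two rules can diverge in a report (constructed example).** Six patients are treated at a dose, two have a DLT, and one of those two refuses the drug on day +10.
- Dose decision under V.7: 2/6 = 33%, so the MTD is exceeded.
- AE/DLT table under the Withdrawal text: (2 − 1)/(6 − 1) = 1/5 = 20%.

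In general, with n treated, a having the event, m excluded and d of those m having the event, the table shows (a − d)/(n − m). This is below a/n whenever d/m exceeds a/n, that is, whenever those who leave early have more toxicity than the rest.

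**6. How many patients could be involved?** From Section V.1 and V.7:
- Evaluable: 18 + 24 + 14 − 6 = 50, the plan's figure.
- Non-evaluable allowance: 10 (phase I) + 3 (phase II) = 13.
- Treated: 50 + 13 = 63, again the plan's figure; 13/63 = 21%.

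This allowance covers every reason for being non-evaluable. Consent withdrawals before day +21 are an unknown part of it.

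**The case against.** **Context.** The sentences before the exclusion concern research samples and the GVHD endpoint, so the authors may have meant only those analyses. The study calendar (Appendix D) also plans day +21 samples from partial withdrawers, which fits poorly with calling every earlier withdrawal full. Both points suggest a narrower intent. Neither changes the sentence, which covers all analyses without qualification and could be applied that way when the report is written.

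**Safety is handled elsewhere.** Section VI has monthly AE review, a grade 3 or higher AE log, and a halt for analysis after four related unexpected grade 4-5 events. V.7 uses DLTs to set the MTD. This stands, and it would be wrong to say that the plan ignores safety. But these are collection and oversight. None is a planned summary of AEs in all treated patients.

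**The stronger reading.** A reader might infer that the exclusion corrupts the dose decision: of two DLT patients in six, one refuses the drug, is replaced by a patient without a DLT, and 2/6 becomes 1/6, although 2 of 7 treated (29%, exact 95% CI 4% to 71%) had a DLT. The documents do not support this. It needs the general Withdrawal sentence to override the specific V.7 rule, and it needs a replacement that V.7 gives only to DLT-free patients.

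Pass probabilities built on that reading are illustration only. With an assumed true DLT rate of 1/3, the chance of at most 1 DLT in 6 is 35%. If an assumed 10% of DLT patients were excluded and replaced, the counted rate is (1/3)(0.9)/(1 − 0.1/3) = 31% and the chance is 40%. The documents give neither input.

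**Timing.** The protocol says accrual is complete, so rewording cannot alter the dose that was chosen. What remains open is how safety is reported.

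**Conclusion.** The point holds for safety reporting. As written, the Withdrawal rule removes treated patients from any AE or DLT summary for a reason that may be toxicity, and V.7 plans no all-treated summary to offset it. The likely direction is to understate toxicity. The size cannot be derived from the documents, because no early-withdrawal rate or event rate is given.

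For the phase I DLT count and the MTD decision, the effect is probably nil; there the issue is inconsistent wording.

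The conclusion assumes that the Withdrawal sentence is applied literally at reporting. It covers only consent withdrawal before day +21. It does not extend to toxicity stops directed by the dose-modification rules, or to DLT-free phase I patients replaced under V.7. Confidence is medium. The change is worth making because the fault is in a stated rule and the remedy is cheap.

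**What to change.** 1. In Section V, Withdrawal, limit the before-day-+21 exclusion to the pSTAT3 and GVHD analyses. State that the V.7 evaluability rule governs phase I and that any DLT before withdrawal counts.
2. In Section V.7, add a summary of AEs and DLTs by assigned dose in every patient who took at least one dose of pacritinib. Include those withdrawn or replaced before day +21, use data up to the date follow-up was refused, and give exact 95% confidence intervals and reasons for stopping early.
3. In the report, show phase I DLTs over all treated patients beside the evaluable count.

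**Cost:** wording in two sections and one recount from the existing AE log, with no added patients, visits or samples. **Downside:** early withdrawers have short follow-up, so their event counts are minimums and should be labelled so.
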